6.4 REPLACEMENT OF PATIENTS

Patients who have been screened but have not been previously randomized to this study may be rescreened for participation if they are eligible.

7 TREATMENTS ADMINISTERED

Children found eligible who do not have documented sleep hygiene training in their history will start a 4-week sleep hygiene and behavioral intervention, which will serve as a wash-out period from any hypnotics with gradual withdrawal during the first 2 weeks and complete withdrawal during the last 2 weeks. Patients will then enter a 2-week SB placebo run-in period. Enough eligible children will be screened for the study to allow for 120 patients to be randomized in a 1:1 ratio to receive Circadin® or placebo at the end of the 2-week SB placebo run-in period, whether they are children who underwent the sleep hygiene and behavioral intervention or not.

Children with a documented history of sleep hygiene and behavioral intervention who are taking prohibited medications will not require additional training and will undergo a 2 week wash-out period before Visit 1 (e.g., Weeks 2 through 0 to wash out melatonin or any other prohibited medications). During these 2 weeks there is no need to complete the sleep and nap diary.

Children with documented history of sleep hygiene and behavioral intervention, who are still found eligible, will enter directly into the 2-week SB placebo run-in period. After the 2-week placebo run-in period, patients who are still found eligible will be randomized in a 1:1 ratio to receive either Circadin® 2 mg or matching placebo for 3 weeks. At the end of the 3-week double-blind period, a decision on dose modification (i.e., an increase to 5 mg) will be made based on predefined criteria ([Section 7.3.1](#)). The double-blind period will continue for another 10 weeks (total 13 weeks) after which Circadin® 2 or 5 mg will be given open-label for another 13 weeks of follow-up to evaluate maintenance of efficacy and safety. At this time point (Week 28), data gathered from both the double-blind and open-label periods will be analyzed. The study will continue with a second opportunity for dose modification according to the same criteria as before (an increase either to 5 mg for patients who are still on 2 mg or to 10 mg for patients who are on 5 mg) after which open-label

treatment will continue for an additional 78 weeks of follow-up to evaluate maintenance of efficacy and safety. At the end of the Circadin[®] open-label period, patients will undergo a 2-week SB placebo run-out period to assess withdrawal effects. A minimum of 90 children are expected to complete the double-blind and first open-label period. A minimum of 50 children are expected to complete the second open-label safety follow-up period.

7.1 PROHIBITED MEDICATIONS

The following medications are not permitted for use for the duration of the study and within 2 weeks prior to Visit 1. If use of these medications is unavoidable for clinical reasons, then the patient will need to be withdrawn from the study:

- Melatonin or melatonin agonists (other than the study treatment)
- Excessive consumption of alcohol

The full list of prohibited medications is given in [Appendix 11](#). This is a living list that will not cause any protocol amendment if needs to be amended.

7.2 INVESTIGATIONAL MEDICINAL PRODUCT

Circadin[®]

Generic name:	Melatonin
Trade name:	Circadin [®]
Chemical name:	N-Acetyl-5-Methoxytryptamine
Formulation:	Amino-methacrylate co-polymer Calcium hydrogen phosphate Lactose Silicon dioxide Talcum Magnesium stearate

The PR of melatonin is achieved primarily by the methacrylate polymer EUDRAGIT. The calcium hydrogen phosphate serves as a filling and binding agent and lactose as a diluent and bulking agent. Talc and magnesium stearate serve as lubricants. Circadin[®] 1 mg minitables will be used in this study. These tablets are 3 mm in diameter and will allow flexibility of dosing for the required dose titrations from 2 mg to 5 mg or 10 mg.

Study drug (IMP) will be stored in the medical center's local pharmacy or in the Investigator's office securely, separate from other drugs (IMP Handling Guidelines). Study drug should not be exposed to direct sunlight or other sources of heat, and is to be kept at room temperature (<25°C).

Placebo

Placebo will be identical in appearance and formulation to active Circadin[®] minitables, but will contain no active melatonin.

7.3 CIRCADIN[®] ADMINISTRATION

The dose will be titrated from 2 mg (2 minitables) to 5 mg (5 minitables – Visit 3) to 10 mg (10 minitables – Visit 5), as instructed in [Section 7.3.2](#).

Circadin[®] and placebo are to be administered orally, 1 portion of minitables daily, taken postprandial at 0.5 to 1 hour before desired bedtime (bedtime should be age-appropriate bedtime). The minitables should be swallowed whole and should not be crushed or halved. Both Circadin[®] and placebo minitables can be administered in foods such as orange juice, semi-skimmed milk, strawberry yogurt, and strawberry jam, to allow dosing of multiple minitables to the children studied. Melatonin was found to be compatible and stable for up to 6 hours in these specific common foods and liquids¹⁶.

7.3.1 Dose Modification

At the end of 3 weeks of double-blind treatment (Visit 3) and 13 weeks of open-label treatment (Visit 5), the Investigator will review the Sleep and Nap Diaries and the eCRF recommendation for dose increase and then make an assessment of treatment effect. If the Investigator decides that a dose increase is necessary, the following criteria must be met before the increase can take place:

- The patient has an absence of SAEs related to study drug.
- The patient has an absence of daytime fatigue related to study drug.
- The parents demonstrated compliance in Sleep and Nap Diary completion (5 out of 7 nights). Compliance means that in at least 5 out of 7 nights per week (total of 2 weeks before each scheduled visit) the parents completed the diary pages with all mandatory questions (i.e., those marked with an asterisk [*], [Appendix 1](#)).
- The patient has received at least 5 of 7 doses in the current week based on Diary-reported data.

AND

- The patient had ≤ 6 hours of continuous sleep AND/OR ≥ 0.5 hours of sleep latency from light off in ≥ 3 out of 5 nights (i.e., in 3 nights or more a week, as a minimum of 5 diaries must be completed each week) in each of the 2 weeks prior to Visit 3 or Visit 5. This will be derived from the Sleep and Nap Diary and calculated by the eCRF.

OR

- The patient had ≤ 6 hours of continuous sleep AND/OR ≥ 0.5 hours of sleep latency from light off only in ≤ 2 out of 5 nights (i.e., in 2 nights or less a week, as a minimum of 5 diaries must be completed each week) in each of the 2 weeks prior to Visit 3 or Visit 5, AND did NOT improve from Visit 2 by at least 1 hour as measured by either shortening of sleep latency or increase in sleep duration or both. Change in sleep duration and sleep latency will be measured

by subtracting the Visit 2 mean duration and sleep latency values from the mean duration and the mean sleep latency values from all available nights 2 weeks prior to Visit 3 or Visit 5. Values will be derived from the Sleep and Nap Diary and calculated by the eCRF. The eCRF will advise whether a dose increase is recommended or not.

If any of the above criteria are not met, or if there is any doubt regarding a criterion, the current dose should be maintained.

Allowed dose increases include 2 mg to 5 mg at Visit 3, and/or 2 mg to 5 mg or 5 mg to 10 mg at Visit 5.

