12.11 HANDLING OF DROPOUTS/MISSING DATA

Missing data will not be replaced for both primary and secondary criteria. The following will be applied concerning start and end dates:

- If the day is unknown and the month and the year are known, it will be replaced by 01 in case of a start date or by the last day of the month in case of an end date.
- If the day and the month are unknown, they will be replaced by 01/01 in case of a start date or 31/12 in case of an end date.
- If the day, the month and the year are unknown, the date will be considered as missing.

For start and end dates of AEs, there is an exception from the above mentioned rules:

- If the day is unknown and the month and the year are the same as the first treatment intake known, it will be replaced by the date of first treatment intake.
- If the day and the month are unknown and the year is the same as the first treatment intake known, it will be replaced by the date of first treatment intake.

At least 3 documented attempts must be made to contact any patient lost to follow-up at any 1 time point prior to the last scheduled contact (clinic visit or telephone contact). One of these documented attempts must include a written communication sent to the patient's last known address via a courier or mail (with acknowledgement of receipt request) asking that they return any unused IMP and return to the clinic/site for final safety evaluations.

Sleep and Nap Diaries should not be amended by site personnel, with exception of the following situations:

- Dates presented with inconsistent formatting can be edited for consistency.
- Missing or incorrect dates in a sequence can be corrected (e.g., the dates Dec 2014 to Jan 2014 could be corrected to Dec 2014 to Jan 2015)
- Time entered using the 12-hour format can be revised to the 24-hour format.
- Hours can be converted to minutes and vice versa, as needed.

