- If at any visit the site determines that parents were not compliant in completing the Sleep and Nap Diaries (i.e., mandatory questions in the diaries were not correctly completed for at least 5 out of 7 nights per week (total of 2 weeks before each scheduled visit), it will be at the discretion of the Investigator to determine whether the patient will be excluded from study as a result of lack of compliance ([Section 6.1](#)). At Visits 1 and 2, this criterion is required to be met for patients to be eligible to continue on study and is considered a major entry criterion. As well, at Visit 3 and Visit 5, if parents were not compliant in completing the Sleep and Nap Diaries the Investigator cannot increase a patient's dose if so desired by the Investigator ([Section 7.3.1](#)). If parents were not compliant in completing the Sleep and Nap Diaries at Visits 3 and 5, this is to be considered a significant violation ([Section 13.3.2](#)) and reported in the eCRF. If a patient visit is delayed the parents are required to continue with completing diaries until the next visit. Compliance will be judged on the diaries completed in the 2 weeks prior to the newly scheduled visit.

The study coordinator should follow-up with parents during the phone calls to ensure diaries are completed in a timely manner and to make all attempts to prevent missing data and/or inconsistent data entry, according to the instructions in the Sleep and Nap Diary Guidelines.

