20 APPENDICES

Appendix 1: Sleep and Nap Diary

This is to be completed by the parent/caregiver daily at home, preferably 2-3 hours after the child wakes up.

Site:	
Subject number:	
NEU_CH_7911 - Sleep and Nap Diary	
	
For all questions below please try to give the exact times and durations however if you do not remember the exact times please give your best estimation	
Date of diary (morning after medication administration)	
Questionnaire completed by	 Mother  Father  Guardian  Caregiver  Other
If completed by other, please specify	
Did the child take his/her medicine last night?	 Yes  No  Unknown
If yes, when? (24 hr clock)	
Comments	
Sleep last night and feeling this morning:	
* What time did the child go to bed last night? (24 hr clock)	
* How long did it take the child to fall asleep (minutes)?	
* How many times did the child wake up in the night?	
* For each wake period please try to provide the exact times and duration awake	
Wake period number	
Wake time (24 hr clock)	
Waking duration in minutes	
Wake period number	
Wake time (24 hr clock)	

Site: Subject number: NEU_CH_7911 - Sleep and Nap Diary		
Waking duration in minutes		
Wake period number		
Wake time (24 hr clock)		
Waking duration in minutes		
* How long did the child stay awake during the night (minutes)?		
* How many hours of actual sleep did the child get that night (hours:minutes)? (This may be different than the number of hours he/she spent in bed)		
* What time did the child wake up? (24 hr clock)		
What time did the child get out of bed? (24 hr clock)		
Can you describe the child's sleep quality last night as one of the following:	 Very bad  Bad  Fair  Good  Very good  Unknown	
Can you describe the child's feeling now as one of the following:	 Very alert  Alert  Quite alert  Tired  Very tired  Unknown	

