If the data entered is inconsistent you will be prompted to update the data, in some cases a comment can be entered to explain why the data entered is inconsistent. The prompt below requires data to be updated.

The page can only be saved when questions with a red star next to them have been answered.

When you have entered the data onto the page, select 'Submit' from the buttons at the bottom right of the screen. This will save the page and take you to a 'Browse' view of the page.

If you were unable to answer any of the questions with a red star, you can select 'Submit as incomplete'. Please note that incomplete diaries might affect suitability to continue in the study.

Once you have entered your Sleep and Nap Diary, you can logout using the logout button at the top right of the page.

Once you have completed entry, the pages will be locked to prevent further editing. If you have made an error and would like to amend any of your diary data after you have saved it, you should contact your site who can unlock the page for you to edit or amend the data on your behalf.

Actiwatch Guidelines for the Parents

General introduction

Actiwatch is a device that will monitor the activity level of your child. It enables your study doctor to determine sleep and activity patterns. It should be worn all night. It should be considered no more intrusive than a wristwatch. The Actiwatch should not be removed except as instructed below.

- Try to acclimate the child to wearing the watch by introducing plastic bracelets and toy watches
- The non-dominant wrist is preferred, the same wrist should always be used every night
- Place the Actiwatch on the subject's wrist and fasten it in such a way as to be slightly snug, but comfortable
- The Actiwatch should be worn for 14 nights before visit 2 and visit 4
- Remember: keep the Actiwatch in a safe place during the day
- Actiwatches are considered water resistant (not water proof). However, please try to avoid showering, bathing, washing the device
- Please stop using the Actiwatch and contact your study doctor in case:
 - skin reddening or inflammation appears
 - the device becomes damaged

What to do at night

- Place the Actiwatch 30 minutes before bedtime
- The Actiwatches display will change when it is put on the wrist.
- After bedtime routine (lights off), press the Marker Button on the Actiwatch - Immediately record this time on the sleep diary as time the child went to bed.

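### A dose increase depends on a diary question that parents may leave blank, so a fully dosed child can be held at 2 mg

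*Protocol*

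**What the plan says.** Protocol 7.3.1 sets two separate diary conditions for an increase at Visit 3 or Visit 5. One is completion: on at least five nights in each of the two weeks before the visit, all questions marked with an asterisk must be answered. The other is dosing: "The patient has received at least 5 of 7 doses in the current week based on Diary-reported data". The default is conservative: "If any of the above criteria are not met, or if there is any doubt regarding a criterion, the current dose should be maintained".

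The dosing count comes from one diary item in Appendix 1, "Did the child take his/her medicine last night", answered Yes, No or Unknown. It has no asterisk. The bedtime, latency, awakening, sleep-hours and wake-time items on the same form do.

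Appendix 2 describes the electronic diary: "The page can only be saved when questions with a red star next to them have been answered". Another button covers the case described as "If you were unable to answer any of the questions with a red star", and such a page is submitted as incomplete. To change a saved page, the parent is told "you should contact your site who can unlock the page for you to edit or amend the data on your behalf".

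On corrections, 12.11 states: "Sleep and Nap Diaries should not be amended by site personnel, with exception of the following situations". The listed situations that allow an edit concern dates, time format and units. Section 14.1 limits changes to parent-reported data to the cases in 12.11. The same section also asks the coordinator to "follow-up with parents during the phone calls to ensure diaries are completed in a timely manner".

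**The concern.** The completion rule and the dosing rule use the same threshold, five of seven, but the form guarantees only the first. A parent can comply fully with the diary and still leave the dose count short. Nothing in 7.3.1 says what to do with a blank, and its default points towards no increase.

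Increases are allowed only at Visits 3 and 5. A child whose sleep criteria call for 5 mg, but who is held at Visit 3 because of a blank, goes through the rest of the double-blind period on 2 mg. That period includes the Week 15 primary assessment of total sleep time. In the Circadin arm this is under-titration caused by a form field. In the placebo arm only the number of minitablets differs. The rule works identically under the blind, so false-positive risk is not affected. A block at Visit 5 falls in the open-label phase and does not touch the primary endpoint.

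**Working it through.** **Inputs from the documents.** Dosing threshold: 5 doses in the current week (7.3.1). Fewest pages the completion rule accepts: 5 per week (7.3.1). Dose item not mandatory (Appendix 1). Save check on starred items only (Appendix 2). After Visit 3 there are 10 more double-blind weeks and then 13 open-label weeks before Visit 5 (5.1).

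**Inputs the documents do not give.** They state no answer rate for the dose item, no page-completion rate and no correction rate. There is no plan figure to reproduce.

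**Step 1: counting.** Let *k* be the pages in the week that could carry a dose answer and *b* the uncorrected blanks. For a child who took all seven doses, reported doses = *k* − *b*, and the rule needs *k* − *b* ≥ 5.

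- *k* = 5: one blank gives 4, which fails.
- *k* = 6: one blank gives 5, which passes; two fail.
- *k* = 7: two blanks give 5, which passes; three fail.

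An Unknown answer acts like a blank. A page submitted as incomplete may still carry a dose answer and so raise *k*.

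**Step 2: failure risk for a given number of pages.** Assume the item is answered independently on a share *p* of completed pages, no blank is corrected, and incomplete pages carry no dose answer. Then P(fail | *k*) = P(Binomial(*k*, *p*) ≤ 4). For *k* = 5 this is 1 − *p*⁵; at *p* = 0.95, 1 − 0.7738 = 0.2262.

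| Pages | *p* = 0.98 | *p* = 0.95 | *p* = 0.90 |
|---|---|---|---|
| 5 | 9.6% | 22.6% | 41.0% |
| 6 | 0.6% | 3.3% | 11.4% |
| 7 | 0.03% | 0.4% | 2.6% |

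**Step 3: averaging over page counts.** Let the number of pages be Binomial(7, *c*), restricted to weeks with at least five, since fewer already fail the completion rule.

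| Nights with a page, *c* | Share with 5 / 6 / 7 pages | *p* = 0.98 | *p* = 0.95 | *p* = 0.90 |
|---|---|---|---|---|
| 95% | 4.1 / 25.8 / 70.1% | 0.6% | 2.0% | 6.4% |
| 90% | 12.7 / 38.2 / 49.1% | 1.5% | 4.3% | 10.8% |
| 80% | 32.3 / 43.1 / 24.6% | 3.4% | 8.8% | 18.8% |

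For *c* = 0.90 and *p* = 0.95: 0.127 × 0.2262 + 0.382 × 0.0328 + 0.491 × 0.0038 = 0.043.

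**Step 4: partial correction.** If half the blanks are filled before the decision, *p* becomes 0.99, 0.975 and 0.95. The *c* = 90% row falls to 0.7%, 1.9% and 4.3%.

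**Step 5: duration.** A missed increase at Visit 3 can next be made at Visit 5: 10 + 13 = 23 more weeks at 2 mg.

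**The case against.** The case against is mainly that several things must coincide. The child must otherwise qualify, dose answers must come from few pages, an answer must be blank, and nobody may notice. With pages on 95% of nights and 95% to 98% of items answered, the risk is only 0.6% to 2.0%, and every rate is assumed. This stands, and it is why the point is minor.

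The plan also has safeguards. The Investigator reviews the diaries at the decision (7.3.1), the coordinator enters paper pages at the visit (Section 8), weekly calls are made (8.6, 12.11), tablets are counted (7.6), eCRFs are reviewed and queried (12.1), and a page can be unlocked (Appendix 2). These will catch some blanks. None is directed at this item, and the tablet count is not the source 7.3.1 names. One can argue that a parent filling a blank is completing the diary rather than amending it. However, a site reading 12.11 and 14.1 strictly would leave it empty.

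The next diary field asks when the medicine was taken, and a time there is also diary evidence of a dose. That narrows the problem where a time was entered without a tick. The documents do not say how such a page is counted.

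Finally, holding the dose without proof of dosing is deliberate, because non-response cannot otherwise be told from non-adherence. That is a sound reason to keep the threshold and the default. It is also a reason to make sure that the question feeding them is answered.

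**Conclusion.** The concern holds as a minor design gap. On the text, a diary that satisfies the completion rule can still fall short on doses. At the five-page minimum, a single uncorrected blank is enough when no other page carries a dose answer.

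The frequency is not known. The weighted range of 0.6% to 18.8% rests on independent answers, all seven doses taken, no correction, and no dose answers on incomplete pages. Correction lowers it. All figures apply only to children who otherwise qualify for an increase. The effect on total sleep time cannot be estimated from the documents.

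**What to change.** - Require an answer (Yes, No or Unknown) to the medicine question on electronic and paper pages from Visit 1 onward, when study drug is taken.
- Keep it outside the diary-compliance criterion. Because 6.1 and 7.3.1 define compliance by the asterisk, use a separate save check and a separate mark on paper.
- At the Visit 3 and Visit 5 diary review, have the site go through this item with the parent before the dose decision.
- Let the parent, not the site, supply a missing answer, on an unlocked electronic page or on the paper page before entry. Say so in 12.11, which also settles the tension with Appendix 2 and 14.1 for this item.
- Leave the five-of-seven threshold and the default to hold the dose as they are.

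The cost is one eCRF check, one line on the paper diary, one item in the two visit reviews and one sentence in 12.11. Parents have one more required answer per page. Paper cannot enforce an answer, so the visit review matters most there. An Unknown answer can still block an increase, and doses on nights without a page remain uncounted.

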6.1 INCLUSION CRITERIA

To be eligible for study entry, all patients must satisfy all of the following criteria at screening:

- Must be children 2 to 17.5 years of age at Visit 2 who comply with taking the study drug.
- Must have written informed consent provided by a legal guardian and assent (if needed).
- Must have a documented history of ASD according to or consistent with the ICD-10 or DSM-5/4 criteria, or neurodevelopmental disabilities caused by neurogenetic diseases (SMS, Angelman syndrome, Bourneville's disease [tuberous sclerosis]) as confirmed by case note review showing that diagnosis was reached through assessment by a community pediatrician or pediatric neurologist or other health care professionals experienced in the diagnosis who took into account early developmental history and school records.
- Must have current sleep problems including: a minimum of 3 months of impaired sleep defined as ≤ 6 hours of continuous sleep AND/OR ≥ 0.5 hour sleep latency from light off in 3 out of 5 nights based on parent reports and patient medical history. (The maintenance and latency problems do not necessarily have to be in the same 3 nights of the week.)
- May be on a stable dose of non-excluded medication for 3 months, including anti-epileptics, anti-depressants (selective serotonin reuptake inhibitors [SSRIs]), stimulants, all mood changing drugs and β -blockers. (Only morning administration of β -blockers is allowed since β -blockers at night have the potential to reduce endogenous melatonin levels and might cause disturbed sleep).
- The sleep disturbance is not due to the direct physiological effects of any concomitant medications such as SSRIs, stimulants, etc.

After completing 4 weeks of sleep hygiene training (for those who need it) and 2 weeks of placebo run-in, patients will be eligible to continue the study if they comply with the following:

- Continue to fulfil sleep problem criteria (see Inclusion Criterion 4) based on the completed Sleep and Nap Diary entered into the electronic case report form (eCRF)

- Parents demonstrate compliance in Sleep and Nap Diary completion (5 out of 7 nights). Compliance means that in at least 5 out of 7 nights per week (total of 2 weeks before each scheduled visit) the parents complete the diary pages with all mandatory questions (mandatory questions are marked with an asterisk [*] in [Appendix 1](#)).
- Continue to fulfil all other eligibility criteria

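### The dose-increase rule in Protocol 7.3.1 leaves out children whose two diary weeks differ, so an unimproved child can lose access to 5 mg by having one more bad night

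*Protocol*

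**What the plan says.** Under Protocol 7.3.1 a bad night is one with 6 hours or less of continuous sleep, a sleep latency of 0.5 hour or more, or both. If the investigator thinks an increase is needed, "the following criteria must be met before the increase can take place". The common criteria are no drug-related SAE, no drug-related daytime fatigue, adequate diary completion and at least 5 of 7 doses taken. One of two sleep branches must also hold:

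- **Branch 1:** 3 or more bad nights "in each of the 2 weeks prior to Visit 3 or Visit 5. This will be derived" from the diary. Improvement is not tested.
- **Branch 2:** 2 or fewer bad nights "in each of the 2 weeks prior to Visit 3 or Visit 5, AND did NOT improve" from Visit 2 by at least 1 hour in sleep latency, sleep duration or both.

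The section then sets the default: "If any of the above criteria are not met, or if there is any doubt regarding a criterion, the current dose should be maintained". It adds that "The eCRF will advise whether a dose increase is recommended or not", and that "Allowed dose increases include 2 mg to 5 mg at Visit 3", with 2 to 5 mg or 5 to 10 mg possible at Visit 5. Section 7 carries the rule forward: "The study will continue with a second opportunity for dose modification according to the same criteria as before".

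**The concern.** Both branches require the same pattern in both weeks, so together they do not cover every child. A child with 3 or more bad nights in one week and 2 or fewer in the other falls between them and is held by the default sentence, whether or not sleep has improved. The outcome is defined, but it does not follow severity.

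Visit 3 is the only visit before the Week 15 endpoint at which the dose can go up. A child held there is next considered at Visit 5, which is 28 − 5 = 23 weeks later, under the same rule.

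Two things are at stake. One is the coherence of the 2/5 mg regimen under test. The other is the reading of the dose outputs: the proportion of children using a maximum of 2 or 5 mg (SAP 3.3) and the diary summaries by final dose (SAP 11.6.2). Some children will appear at 2 mg because of how their bad nights fell across two weeks, not because 2 mg was enough.

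**Working it through.** **1. The rule as written.** Let w1 and w2 be the bad nights in the two weeks. Assume the common criteria are met and the investigator wants an increase. Then:

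- Branch 1 = (w1 ≥ 3 and w2 ≥ 3)
- Branch 2 = (w1 ≤ 2 and w2 ≤ 2 and improvement under 1 hour)
- Increase allowed = Branch 1 or Branch 2

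**2. All week pairs.** With 5 completed diaries a week (the minimum) there are 6 × 6 = 36 pairs. With 7 there are 8 × 8 = 64.

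| Child | Diaries per week | Eligible pairs | Held pairs |
|---|---|---|---|
| Unimproved | 5 | 18 | 18 |
| Unimproved | 7 | 34 | 30 |
| Improved by 1 hour or more | 5 | 9 | 27 |
| Improved by 1 hour or more | 7 | 25 | 39 |

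For unimproved children every held pair is mixed, and every mixed pair is held. The pair counts describe the rule; they are not frequencies of children.

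**3. Order check, unimproved child.** One extra bad night removes eligibility in six steps: 2+0 to 3+0, 2+1 to 3+1, 2+2 to 3+2, and the same three with the weeks swapped. The highest held totals are 5+2 = 7 bad nights with 5 diaries and 7+2 = 9 with 7. A 0+0 child may be increased. Because branch 1 does not test improvement, a 3+3 child who gained an hour may also be increased while an unimproved 5+2 child may not.

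**4. Other routes.** Reading the list as (common criteria and branch 1) or branch 2 changes nothing, because mixed weeks fail both branches. Section 7.3.2 lets the investigator restart a previous dose, but only after a reduction. No other section of the protocol or SAP deals with mixed weeks.

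**5. How common mixed weeks might be.** The documents give no nightly rate, so this part rests on assumptions. Suppose each night is bad independently with probability p, and n diaries are completed each week. Let q = P(Binomial(n, p) ≥ 3). The mixed share is 2q(1 − q). For n = 7 and p = 0.6, q = 0.904, so the share is 2 × 0.904 × 0.096 = 17.4%.

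| p | n = 7 | n = 6 | n = 5 |
|---|---|---|---|
| 0.6 | 17.4% | 29.4% | 43.3% |
| 0.7 | 5.6% | 13.1% | 27.3% |
| 0.8 | 0.9% | 3.3% | 10.9% |

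The value 0.6 is the entry threshold in Protocol 6.1, "sleep latency from light off in 3 out of 5 nights based on parent reports and patient medical history", taken as near-baseline for a child who has not improved. Seven diaries a week is the target, since the diary covers 14 nights before each visit (Table 5-2, footnote 6).

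If p also varies between children (Beta distribution, mean 0.6, 0.7 or 0.8):

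| n | SD of p | mean 0.6 | mean 0.7 | mean 0.8 |
|---|---|---|---|---|
| 7 | 0.15 | 20.2% | 11.2% | 5.5% |
| 7 | 0.25 | 17.5% | 12.1% | 7.2% |
| 5 | 0.15 | 34.3% | 24.8% | 14.2% |
| 5 | 0.25 | 23.9% | 18.2% | 11.0% |

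More moderate rates make mixed weeks more common. With 7 diaries and independent nights the share is 35% at p = 0.5 and 49% at p = 0.4.

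**The case against.** The best defence is that the protocol does give an instruction: when a criterion fails or is in doubt, hold the dose. Both branches ask for the same pattern in both weeks, so holding when the weeks disagree could be a deliberate demand for consistency. The consequences are also limited. The rule is blind in both arms, and the outputs it touches are exploratory or descriptive. Final dose already depends on adverse events, diary compliance, doses taken, investigator judgement and discretionary reductions. The size estimate is driven by assumptions, and a mid-trial change would create two titration rules.

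Much of this stands. No site lacks an instruction, no confirmatory conclusion changes, and the number of children affected is unknown. The figures above bound that number only for the assumed rates of 0.6 to 0.8.

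The consistency argument does not stand. An unimproved child whose weeks both looked like the better one would qualify under branch 2, and one whose weeks both looked like the worse one would qualify under branch 1. Doubt about which week is typical therefore gives no reason to withhold the increase. General caution does not explain it either, because branch 2 already allows increases in children with fewer bad nights. Other influences on final dose do not justify adding one that runs against severity.

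**Conclusion.** The concern holds. As written, 7.3.1 bars every mixed-week child from an increase, including unimproved children with up to 9 bad nights in 14, while allowing an increase in unimproved children with none. This follows from the text alone and needs no assumption.

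The size does need assumptions. For nightly rates of 0.6 to 0.8, the mixed-week share runs from 0.9% to 20% with 7 diaries a week and from 11% to 43% with 5, across the independent and between-child models. Within those assumptions these are ceilings on the children affected, because only mixed-week children who also gained less than 1 hour, met the common criteria and were judged to need more drug lose anything.

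The primary treatment comparison is not biased. The rule should be corrected for the sake of the titration and the dose summaries. The eCRF algorithm is not in the documents. If it handles mixed weeks differently, it departs from the written rule, and the text would still need correcting.

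**What to change.** Reword the opening of branch 2 so that it applies to any child who does not meet branch 1, that is, a child with 2 or fewer bad nights in at least one of the two weeks, and keep the requirement of less than 1 hour of improvement from Visit 2. Leave the safety, diary, dosing and investigator-judgement conditions and the default sentence as they are.

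Under this wording every unimproved pair is covered (36 of 36 with 5 diaries, 64 of 64 with 7) and no extra bad night removes eligibility. Improved children are treated exactly as now. Deleting branch 2 would also restore the order, but it would take away the increase now open to unimproved 2+2 children.

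The trade-off is that somewhat more unimproved children become eligible for 5 mg, or for 10 mg at Visit 5, subject to the existing safeguards. The change needs a protocol amendment with ethics approval (Protocol 13.3.1). If the eCRF recommendation follows the current text, that calculation must be reprogrammed and revalidated (Protocol 7.3.1 and 12.1). No new data are collected.

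The change is best made before enrolment. The SAP already cites protocol version 6.0 Amendment 5, so that may no longer be possible. If it is made mid-trial, record the effective date and flag which version of the rule applied to each child, so that the final-dose tables can be read accordingly.
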